DRUG USE INVESTIGATION FOR HIV INFECTION PATIENTS OF MARAVIROC

- HRD Joint Survey -

STATISTICAL ANALYSIS PLAN

CELSENTRI Tablets 150 mg Statistical Analysis Plan

Outsourced by
Product name
Pregnant Women
Prepared by

ViiV Healthcare K.K.
CELSENTRI Tablets 150 mg Drug Use Survey, Special Drug Use Survey for
CMIC-PMS Co., Ltd. PPD

<General Definitions>

Re-examination period	
Number of report	Survey period
1st	2008/12/25 (H20) - 2009/2/5
2nd	2/6/2009 (H21) - 8/5/2009
3rd	8/6/2009 (H21) - 2/5/2010
4th	2/6/2010 (H22) - 8/5/2010
5th	8/6/2010 (H22) - 8/5/2011
6th	8/6/2011 (H23) - 8/5/2012
7th	8/6/2012 (H24) - 8/5/2013
8th	8/6/2013 (H25) - 8/5/2014
9th	8/6/2014 (H26) - 8/5/2015
10th	8/6/2015 (H27) - 8/5/2016
11th	8/6/2016 (H28) - 8/5/2017
12th	8/6/2017 (H29) - 8/5/2018
13th	8/6/2018 (H30) - 12/24/2018
Re-examination	12/25/2008 (H20) - 12/24/2018
Date conversion	
When you calculate dates for aggregation, make the following replacement: Replace the date “AA=early in the month” with 05, “BB=middle of the month” with 15, “CC=late in the month” with 25, and “DD=around” with 01. Replace “20EEEEEE=continued” with “the outcome confirmation date of the patient”. If nothing is provided, enter “entry date”. The new survey does not have entries of 20EEEEEE, but enter 20EEEEEE for continued administration if “entry date” is found. When you need to replace any inappropriate date (such as Day 00), add the following process: When the date in “first administration date” is not appropriate as a date, choose the final date of the month. When the month and date in “first administration date” are not appropriate as a date, enter “1231”. When the date in “final administration date” is not appropriate as a date, enter “01”. When the date in “onset date of adverse event” is not appropriate, enter “01”. When the date in “laboratory test date” is “00” or “99”, enter “01”. Only a date after the approval date (=December 25, 2008) should be used for CELSENTRI Tablets (when the first administration date comes before the approval date, replace it with the approval date).

Date unit	A week has 7 days, a month has 30 days, and 1 year has 365 days.
Prior to administration	It should be within 30 days prior to the first administration of CELSENTRI Tablets and be the closest date to the first administration date (the administration date is also included).
Displayed digit	Decimal numbers should be rounded to the second decimal place.

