Tropism classification at the first administration of CELSENTRI Tablets.	Display the value obtained on the closest date to the first administration date of CELSENTRI Tablets within 30 days before/after the first administration. Display the earlier value obtained for this if the same values are found on the same dates both before and after the first administration. [Stratification] R5, X4, DM, NR, Not implemented* *If it was not conducted, separately record the reason for this (Prepare a list of the reasons why the tropism assay was not conducted).
Presence/absence of concomitant treatment	If any concomitant treatment was given in the “administration period” of CELSENTRI Tablets (for ≥1 day), select “present”. [Stratification] Absence, Presence, Unknown/not provided
Presence/absence of blood coagulation factor	Count the presence/absence of drugs administered while the patient was on CELSENTRI Tablets 150 mg (the drugs with the concomitant drug codes {6343406, 6343409, 6343429, 6343430, 6343414, 6343431, 6343432, 6343434} on the top). In addition, display the presence/absence when “present” was selected for the presence/absence of haemophilia. [Stratification] Absence, Presence, Unknown/not provided

*When the minimum/maximum are specified in the stratification of the mock-up, display the minimum/maximum of each item.

<<Handling of cases>>

Patients whose survey form was collected	On March 26, 2018, the data on all the patients registered during this survey period were locked. Therefore, they are the patients whose survey form was collected as of March 26, 2018.
Patients in the safety analysis group	
Patients excluded from the patients applicable to the following [Exclusion criteria from the safety analysis group] (Note that the patients with adverse reactions are not excluded).
 
[Exclusion criteria from the safety analysis group]
 
[1] Not visited after the first visit ⇒Patients whose survey form is composed of 1 volume alone, with “Outcome of patient” of “1. Not visited” or “2. Transferred”, and also with their first administration of CELSENTRI Tablets = the outcome confirmation date in “Outcome of patient”.
 
[2] Not administered ⇒Patients whose administration of CELSENTRI Tablets cannot be traced since the approval date (=December 25, 2008).
 
[3] Unable to re-survey adverse events ⇒ “8 Unknown” and “0. Not provided” for the presence/absence of adverse events”

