In the list of *, use a row for an adverse reaction; enter multiple adverse reactions in the equivalent number of rows for a patient. Entry of a patient number, etc. should be repeated.

4) Table for “Patients in the efficacy analysis group”

A table and a chart of changes in HIV-RNA load/CD4	
Prepare a chart and table on the changes in HIV-RNA load/CD4 in patients with and without treatment history, with and without concomitant CYP3A inhibitors, sex, with and without complications, with and without concomitant drugs, CDC classification and for all patients in the efficacy analysis group.
 
Pre-administration (Month 0) should be the most recent date within 30 days before administration including the first administration date.
 
For post-administration (Month 3, 6, 9, etc.), choose the value obtained on the most recent date within ±45 days from each point of Month 3, 6, 9, etc. If a “test value” is missing either before or after administrations, it should not be included in the chart.
 
Use a line chart with test values on the y-axis and months after administration (for every 3 months) on the x-axis.
 
For each point, extend the whisker in a single direction to show the SD value.
 
When you have n=1 for each point, display it with a dot without connecting it with a line.
 
Of note, for the maximum number of HIV-RNA copies detected, replace it with 399 from the initiation of survey to March, 2008, with 39 from April, 2008 to 2010 and with 19 in and after 2011 (depends on the site). Handle the encoded values, etc. as follows: Replace the values with inequality sign with the following [1] to [3] in calculation:

--	--

	
[1] <400: The value that you subtract 1 from the figure without inequality sign. Note that the inequality sign must be removed from the figures with inequality sign. For example: change "<20" to "19", "<40" to "39", "≤20" to "20", "≤40" to "40"
 
[2] ≥400 and <100000: Missing
 
[3] ≥100000: the value without inequality sign. For integer values less than 400 with no inequality sign, use them as they are without replacement.

Patients included in the chart [data in each plot]	Display the patient registration numbers and test results for each point of Month 0, 3, 6, 9, etc. to the number of HIV-RNA copies and CD4, the output data in the above graph.

5) Changes in tropism

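### Read literally, the HIV-RNA/CD4 chart rule takes the latest test in each ±45-day window, not the nearest; the wording allows either and should be settled

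*SAP*

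**What the plan says.** SAP section 4), in the row on changes in HIV-RNA load and CD4, plots a value every three months: "Use a line chart with test values on the y-axis and months after administration (for every 3 months) on the x-axis". The baseline rule in that row is "Pre-administration (Month 0) should be the most recent date within 30 days before administration including the first administration date". For the later points the instruction is to "choose the value obtained on the most recent date within ±45 days from each point of Month 3, 6, 9, etc". No tie rule is given, and no rule for a test that falls in two windows. Under General Definitions, the Date unit row reads "A week has 7 days, a month has 30 days, and 1 year has 365 days".

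Two other rows choose one value from a window:

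- **General Definitions, Prior to administration.** This covers the same 30 days before first administration as Month 0, but says the value should "be the closest date to the first administration date (the administration date is also included").
- **Handling of items, tropism at first administration.** This window is two-sided: "Display the value obtained on the closest date to the first administration date of CELSENTRI Tablets within 30 days before/after the first administration". It has a tie rule: "Display the earlier value obtained for this if the same values are found on the same dates both before and after the first administration".

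SAP section 5) lists tropism results within ±45 days of the same three-monthly points and does not ask for a single value. Protocol 7.7 collects the date of each test. Neither document sets a testing interval.

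**The concern.** At Month 0 the window lies wholly before treatment, so the most recent test is also the closest one. Around Month 3, 6 or 9 the window extends on both sides of the target, and the two words part company. Taken literally, *most recent* passes over a test on the nominal day in favour of one up to 45 days later. The more often a patient is tested, the nearer the selected value lies to the end of the window.

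The same row asks for curves by treatment history, CYP3A inhibitor use, sex, complications, concomitant drugs and CDC classification. Protocol 8.2(2) uses such tabulations to look for factors affecting efficacy. If the charted groups were tested at different frequencies, their curves would share a month label but not a true time. Where values are still changing, that could imitate or mask a difference. The patient-level listing that accompanies the chart specifies registration numbers and test results for each point but names no test date, so a reader might not notice.

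**Working it through.** The plan states no figure for this point, so there is none to reproduce. The check builds the windows from the SAP's own rules and then applies both readings.

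**1. Windows.** Inputs: 30-day months (SAP Date unit), points every three months and ±45 days inclusive (SAP section 4). Day 0 is taken as first administration.

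- Month 3: 90 ± 45 = days 45 to 135
- Month 6: 180 ± 45 = days 135 to 225
- Month 9: 270 ± 45 = days 225 to 315
- Month 12: 360 ± 45 = days 315 to 405

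Each window is 91 days wide and the points are 90 days apart, so neighbours share exactly one day: 135, 225, 315 and so on.

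**2. One patient, tests on days 28, 56, 84 and so on (assumed).**

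| Point | Tests in window | Latest | Closest |
|---|---|---|---|
| Month 3 (day 90) | 56, 84, 112 | 112 (22 late) | 84 (6 early) |
| Month 6 (day 180) | 140, 168, 196, 224 | 224 (44 late) | 168 (12 early) |
| Month 9 (day 270) | 252, 280, 308 | 308 (38 late) | 280 (10 late) |

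**3. Average over all starting phases.** With regular testing every k days, k up to 90, the last test in the window falls between 0 and k days before the window closes, k/2 on average. The mean delay is therefore about 45 - k/2. In whole days the last test is 0, 1, ..., k - 1 days before the close, which gives 45 - (k - 1)/2. Every phase was enumerated over Months 6 to 36. The intervals are assumptions.

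| Interval k (days) | 45 - k/2 | Latest date, whole days | Closest date, whole days |
|---|---|---|---|
| 14 | 38 | +38.5 | -0.5 |
| 28 | 31 | +31.5 | -0.5 |
| 42 | 24 | +24.5 | -0.5 |
| 60 | 15 | +15.5 | -0.5 |
| 84 | 3 | +3.5 | -0.5 |
| 90 | 0 | +0.5 | -0.5 |
| 91, 120, 180 | not applicable | 0 | 0 |

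From 91 days upward a window holds at most one test, so the two rules agree. The -0.5 arises from giving ties to the earlier date.

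**4. Does the shared day cause the delay?** No. Shortening the windows to -45 to +44 days while keeping the latest-date rule moves the mean delay at k = 28 only from 31.5 to 30.5 days.

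**5. When does one test serve two points?** Under the latest-date reading, a day-135 test is the Month 3 value. It is also the Month 6 value only if no test falls on days 136 to 225, which means the next test is more than 90 days later. In the enumeration this never happened at intervals of 90 days or less. It happened in 10 of 910 adjacent pairs at 91 days (1.1%) and 10 of 620 at 120 days (1.6%). At 180 days only 20 adjacent pairs had both points filled, and 10 of those were repeats. For the later point, such a value is 45 days early, not late. With windows of -45 to +44 days the count is zero.

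**The case against.** The strongest reply is that *most recent* here simply means *nearest*. The SAP describes the same baseline window once as *most recent* and once as *closest*, so its author may use the words interchangeably. The text also looks like a translation, since Japanese characters remain in the Administration period rows. This stands as far as intent goes: a reader might infer that the plan deliberately chose the latest value, and the documents do not establish that. It does not settle the instruction, because the baseline window is one-sided and the two words cannot disagree there. The only other two-sided window with a selection rule says *closest*.

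A reader might also infer that the shared days make the points run late. They do not (steps 4 and 5). Under regular testing, the patients tested often enough to run late are not those whose test can be used twice.

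A third tempting inference is that the subgroup curves are biased by about a month. No document gives a testing interval, shows that testing frequency differs by stratum, or says how fast values change. A distorted comparison needs the literal reading, unequal testing frequency and changing values together.

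Finally, the output is a descriptive chart and table with no test specified at these points, and Protocol 8.2(1) makes adverse drug reactions the primary analysis items. This stands and limits the importance of the point. Section 5) selects no single tropism value, so a boundary-day result would merely be listed under two months.

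**Conclusion.** The selection rule is ambiguous, and its literal reading departs from the plan's own practice for a two-sided window. If it is programmed literally, plotted points are late on average by about 45 - k/2 days for patients tested every k days: roughly a month at four-weekly testing, two weeks at two-monthly testing, and nothing at 90 days or longer. The closest-date rule stays within half a day of zero at every interval examined. These figures assume regular testing at random phase. The actual shift in this survey cannot be found from the documents, and patients with a single test in a window are unaffected by the selection rule.

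A shift between strata is possible but not shown. It would matter only for reading the efficacy curves, and the primary safety analysis is untouched. The shared boundary day is a separate and smaller fault, confined to patients whose next test is more than 90 days away. The point deserves correction because it is cheap to correct, not because a bias has been demonstrated.

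**What to change.** In SAP section 4), replace the post-administration rule with: *use the value on the date closest to day 90, 180, 270, etc. (the earlier date if tied), with windows running from 45 days before to 44 days after each point so that no test falls in two windows.* Use the same windows for the tropism list in section 5) for consistency.

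The cost is the SAP wording and minor programming. No new data are needed, since Protocol 7.7 already collects test dates. The SAP reports that the data were locked on March 26, 2018. If the chart has already been produced, state which reading was programmed, rerun it if the latest date was taken, and record that the change was made after lock.

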8.2 Analysis Methods

(1) Analyses related to safety evaluation

In the safety analysis set, the primary analysis items will be the occurrence of common ADRs and the incidence of ADRs (proportion of patients with AEs with which Celsentri's causal

relationship could not be denied). In addition, when tabulating the incidence of ADRs by factor such as patient background characteristics, factors affecting the onset of ADRs will be also examined.

(2) Analyses related to efficacy evaluation

Efficacy parameters for anti-HIV drugs such as a CD4 count, number of HIV-RNA copies and CDC classification will be tabulated and analyzed by patient background characteristic to examine factors affecting the efficacy of Celsentri. In patients tested for tropism, the relationship with the status of tropism change will be also evaluated.

9. Organization System for the Implementation of the Survey

The survey will be conducted using the system described in Appendix 3 in accordance with the procedures for the implementation of the HRD cooperative investigation (Appendix 2). The procedures for notifying ADRs, etc. are presented in Appendix 4.

This survey will be performed as a cooperative investigation by companies marketing drugs for the treatment of HIV infection^{Note 1)} using a common CRF. The common CRF for the drug use-results survey may be completed one copy for one patient even if a few anti-HIV infection drugs are coadministered during the reexamination period.

10. Name and Address of the Contractee, and the Scope of the Concerned Outsourced Activities

(1) Contractee

Address: PPD [redacted]

Name: PPD [redacted], PPD [redacted] CMIC PMS Co., Ltd.

Name of the person responsible for implementation: PPD [redacted], Postmarketing Surveillance Operation Implementation Supervisor

(2) Scope of outsource activities

- 1) Request to and contract with institutions
- 2) Issuance of a user's ID and password to each investigator
- 3) Retention of the originals of enrollment forms
- 4) Sending the copies of enrollment forms
- 5) Verification of registration and investigation items entered and sent by the investigators
- 6) Collection of the originals of CRFs
- 7) Preparation and collection of the statement of confirmation
- 8) Sending the copies of CRFs
- 9) Arranging reinvestigation items
- 10) Request for a reinvestigation
- 11) Retention of the originals of CRFs
- 12) Sending the CRFs (final version)
- 13) Data locking
- 14) Coding
- 15) Data tabulation/analyses

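### The SAP text specifies CD4 levels with an SD whisker but no within-patient change from Month 0 and no interval, so the precision of a change is not shown and the plotted trend can partly reflect a changing patient set

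*SAP*

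**What the plan says.** Protocol 8.2 (2) names CD4 count among the efficacy parameters, to be "tabulated and analyzed by patient background characteristic to examine factors affecting the efficacy of Celsentri".

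The SAP carries this out in its table section 4), for the efficacy analysis group: "Prepare a chart and table on the changes in HIV-RNA load/CD4 in patients with and without treatment history", followed by several further strata and all patients together. The selection and display rules are:

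- Baseline: "Pre-administration (Month 0) should be the most recent date within 30 days before administration including the first administration date".
- Later points: "choose the value obtained on the most recent date within ±45 days from each point of Month 3, 6, 9, etc".
- Missing values: "If a “test value” is missing either before or after administrations, it should not be included in the chart".
- Display: "Use a line chart with test values on the y-axis and months after administration (for every 3 months) on the x-axis".
- Spread: "For each point, extend the whisker in a single direction to show the SD value".
- Sparse points: "When you have n=1 for each point, display it with a dot without connecting it with a line".

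A companion listing gives each patient's result at every point. The columns of the accompanying table are not described. The Test entry in the SAP's General Definitions covers exclusions and the chi-square and Fisher's exact tests; it has no rule for a continuous change.

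**The concern.** The output is titled as changes, but the only quantity described is the level at each point. Three things follow.

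- **Precision.** An SD whisker shows how much patients differ from one another. It does not show how well the mean change is known, and a reader cannot derive that from the plotted SDs without the within-patient correlation, which is not reported.
- **Composition.** If the patients behind the Month 0 point are not those behind a later point, the difference between the two means mixes real change with a change in who is counted.
- **Strata.** Groups such as those with and without treatment history may start at different CD4 levels. Level curves with SDs give no measure of uncertainty for a difference in gain, which is what the protocol's question about factors affecting efficacy calls for.

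**Working it through.** **Inputs.** The documents give no CD4 SD, number of patients per point, correlation between visits or target, so there is no planned figure to reproduce. Every numerical input below is an assumption, and CD4 values are in cells/mm3.

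**1. Whisker against precision of the change.** Let r be the correlation between a patient's Month 0 and later value, with the same level SD at both.

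SD of change = SD × √(2(1 − r)); 95% half-width = 1.96 × SD of change / √n.

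With level SD 200 and n = 50:

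| r | SD of change | 95% half-width | SD whisker |
|---|---|---|---|
| 0.5 | 200.0 | 55.4 | 200 |
| 0.7 | 154.9 | 42.9 | 200 |
| 0.9 | 89.4 | 24.8 | 200 |

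Over n = 20 to 100, SD = 150 to 250 and r = 0.5 to 0.9, the half-width runs from about 13 (n = 100, SD 150, r = 0.9) to about 110 (n = 20, SD 250, r = 0.5). The same whisker is compatible with quite different precision.

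**2. Same patients at both points.** The difference between the two means then equals the mean of the individual changes. A simulated set of 50 pairs gave 53.0 both ways. Direction and size can be read from the chart in this case.

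**3. Does the plan ensure the same patients?** The missing-value rule can be read visit by visit, or as requiring any one later value. Under either reading, a patient with a Month 3 value but none at a later point can stay in the Month 0 mean. A single line has one Month 0 point, which can match every later point only if the same patients are present throughout. The plan allows for points with n = 1, so it does not assume constant numbers.

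**4. Size of the effect when the sets differ.** Five patients at 100, 200, 300, 400 and 500, all unchanged, with the two lowest absent later: the plotted mean goes from 300 to 400 and the SD from 158 to 100. The mean change in the three pairs is 0.

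For a normal baseline with mean 300 and SD 200, no change in any patient, and the lowest fraction f absent later:

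apparent rise = SD × φ(z_f) / (1 − f), where φ is the standard normal density and z_f the normal quantile at f.

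- f = 10%: 200 × 0.1755 / 0.9 = 39
- f = 20%: 200 × 0.2800 / 0.8 = 70
- f = 30%: 200 × 0.3477 / 0.7 = 99

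Simulation gave 39.0, 69.9 and 99.2. If individual values vary around an unchanged overall mean, the artefact is smaller: with 20% absent it is about 35, 49 and 63 at r = 0.5, 0.7 and 0.9.

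**5. What pairing does not cure.** In the same simulation at r = 0.7 with the lowest 20% absent, the mean paired change among those remaining is −21.0, although the overall mean did not change. This is regression to the mean under selective loss. Pairing removes the comparison of different patients, not all dropout bias.

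**The case against.** The case for leaving the plan alone is substantial. This is a descriptive drug-use survey whose primary analysis items concern adverse drug reactions. It has no CD4 hypothesis, target or sample-size basis, and a mean with SD is a legitimate description. The patient listing holds what is needed to compute paired changes. Adding intervals has a cost: counting all patients, two groups for each of five factors and CDC classes A, B and C gives 1 + 10 + 3 = 14 groups. The eight-year enrolment period would allow up to 8 × 4 = 32 quarterly points, so as many as 14 × 32 = 448 unadjusted intervals, with late points sparse.

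All of this stands, and it limits the weight of the point. It does not supply the missing precision or settle which patients form the Month 0 mean.

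A reader might infer more than the documents support:

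- **That the chart cannot show whether CD4 rose, or by how much.** It can, descriptively, and exactly so when the same patients contribute.
- **That the output contains no change from baseline.** A table of changes is ordered, its columns are not given, the mock-ups are not in the documents, and the SAP says table forms may change. Only the silence of the SAP text can be stated.
- **That paired data will be analysed as unpaired.** No two-sample test or interval for CD4 is planned.
- **That the whiskers will always overlap, or that strata cannot be compared on gain.** Overlap depends on unknown data, and the stratified charts and listing allow a descriptive comparison.

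**Conclusion.** The concern holds as a reporting gap. The SAP text specifies CD4 levels with an SD whisker, and nowhere specifies a within-patient change from Month 0 or an interval. The chart conveys direction, but not the precision of a change, and it does not guard against a changing patient set.

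The apparent rise of 39 to 99 cells/mm3 rests on an assumed baseline mean of 300 and SD of 200, on loss confined to the lowest 10% to 30%, on no change within any patient, and on the absent patients still counting at Month 0. It shows what could happen; it is not an estimate for this survey. Loss unrelated to CD4 would produce no systematic rise.

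The improvement is worth making because it is cheap and serves the protocol's stated purpose. It concerns a secondary, descriptive output and leaves the primary adverse drug reaction analysis untouched.

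**What to change.** In SAP section 4), for CD4:

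1. At each 3-month point, add to the table the number of patients with both a Month 0 value and a value at that point, their mean change from their own Month 0, and its 95% CI, overall and for each listed stratum.
2. Plot the mean change with its CI as a second panel. Keep the level chart with SD as description.
3. Label the intervals descriptive and unadjusted for multiplicity. Where n is too small, including n = 1, show n without an interval.
4. Note beside the table that the paired change describes the patients still observed at that point and does not remove bias from selective loss.

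The values are already selected for the chart and listing, so no new data are needed. The cost is some extra table columns and one panel, many unadjusted intervals, and sparse late points that must be read with care.

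### HIV-RNA is plotted in copies with an SD whisker, with no stated centre statistic and no proportion suppressed, so the chart may rank strata against the share suppressed (low severity)

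*SAP*

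**What the plan says.** Protocol 8.2(2) tabulates CD4, HIV-RNA copies and CDC classification by background characteristic, in order to look for factors that influence efficacy. For HIV-RNA the planned means is SAP section 4, one table and chart of changes over time, overall and by stratum (treatment history, CYP3A inhibitor use, sex, complications, concomitant drugs, CDC class).

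- **Axis:** "Use a line chart with test values on the y-axis and months after administration".
- **Spread:** "For each point, extend the whisker in a single direction to show the SD value".
- **Unit:** copies. The listing of the plotted data reads "Display the patient registration numbers and test results for each point of Month 0, 3, 6, 9, etc. to the number of HIV-RNA copies", and protocol 7.7 collects the same quantity. The substitution values for results below the detection limit (399, 39, 19) are also in copies.
- **Not stated:** the centre statistic (mean, median or geometric mean) and whether values are transformed. The SAP does name mean and SD for age.
- **Not planned in either document:** a proportion of patients suppressed.

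Results carrying an inequality sign follow three rules. Below 400 they are replaced by a nearby number. The second rule is "2] ≥400 and <100000: Missing" and the third is "3] ≥100000: the value without inequality sign". Neither of these two limits the direction of the sign. A missing test value is left out of the chart.

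**The concern.** On treatment, many HIV-RNA results may sit at the detection limit while a few run to tens of thousands of copies. A raw mean of such data mostly reports the size of the largest values, and its SD does the same. If that is what the chart shows, a stratum with more patients suppressed can look worse because of one patient. Comparing strata is the purpose of the display, so this weakens the HIV-RNA part of the efficacy description.

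The second rule raises a smaller, separate question. A result above an upper assay limit comes from a viraemic patient. Removing it when the limit lies from 400 to below 100,000, but keeping it at 100,000 or more, makes inclusion depend on the assay ceiling.

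**Working it through.** The documents give no HIV-RNA summary figure, stratum size or load distribution, so there is nothing to reproduce. Everything below except the rules and the value 19 is assumed. Suppressed means ≤40 copies; on log10, every suppressed result is set to 40.

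**1. Can the order reverse?** Take three strata of 50.

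| Stratum | Suppressed | Raw mean | SD | log10 mean | Median |
|---|---|---|---|---|---|
| A: 49 at 19, 1 at 100,000 | 98% | 2,018.6 | 14,139 | 1.670 | 19 |
| B: 45 at 19, 5 at 1,000 | 90% | 117.1 | 297 | 1.742 | 19 |
| C: 48 at 19, 2 at 1,000 | 96% | 58.2 | 194 | 1.658 | 19 |

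- Mean A = (49×19 + 100,000)/50 = 100,931/50 = 2,018.6. Mean B = (45×19 + 5×1,000)/50 = 5,855/50 = 117.1. Mean C = (48×19 + 2×1,000)/50 = 2,912/50 = 58.2.
- A against B: the better-suppressed stratum has a raw mean 2,018.6/117.1 = 17.2 times higher. A reverses with B once its one viraemic patient exceeds 5,855 − 49×19 = 4,924 copies. The log10 mean ranks this pair correctly.
- A against C: the raw mean and the log10 mean both rank opposite to the proportion.
- The proportions themselves barely differ (Fisher p = 0.20 for A against B, 1.0 for A against C). The examples show direction only.
- The median is 19 in all three, so it separates none of them.

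**2. How often?** Simulation of 20,000 pairs per cell over 36 cells. Viraemic shares were 5 vs 10%, 5 vs 20%, 10 vs 20% and 10 vs 30%, with n = 25, 50 or 100 per stratum. Viraemic loads were log10-uniform on 41 to 10^5.5, 10^2.5 to 10^5, or 41 to 10^4, with the same range in both strata.

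- Summary contradicts the observed proportion, untied pairs: raw mean about 2% to 24%, log10 mean 0% to 8%.
- Against the true order at n = 50, 10 vs 20%: raw mean wrong in about 21% to 25% of pairs, log10 mean in 9% to 11%, proportion in about 6% (with about 4% ties).
- A separate run with 90% vs 70% suppressed, n = 10 to 100, and unsuppressed log10 loads normal with mean 3.5 and SD 0.7 to 1.0 gave 8% to 18% for the raw mean. The log10 mean gave 0.02% to 2.7%. Both are among runs where the truly better stratum also had the higher observed share.

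**3. The inequality rules, applied literally.** `>400`, `>50000` and `>99999` become missing; `>100000` becomes 100,000. Suppose a stratum has 18 results `<20` (recorded as 19) and two above an upper limit.

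- Two at `>50000`: both dropped, leaving 18 values with mean 19, all suppressed.
- The same two kept at their bound: (18×19 + 2×50,000)/20 = 5,017, with 18/20 = 90% suppressed.
- Two at `>100000`: kept by the plan, mean (18×19 + 2×100,000)/20 = 10,017.

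The documents do not say whether any such results exist. If none do, the effect is zero.

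**The case against.** The strongest reply is that the harm depends on a statistic the SAP does not name. The mock-ups may name it, and the closing note lets table forms change. That stands: a reader might infer that the SAP specifies a raw mean, but the text supports only that the SD whisker and the copies unit point that way. A reader might also infer that the unit is missing. It is not; what is unnamed is the centre statistic and any transformation.

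The simulation can be over-read too. Its largest raw-mean error against the true order, 31.6%, comes from 5 vs 10% viraemic with 25 per stratum. There the proportion is also wrong in about 17% of pairs and tied in about 18%, so much of that figure is small-sample noise. Contradiction of the observed proportion is the fairer measure.

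In the worked example, an SD of about seven times the mean, together with the listing of plotted values, would alert a careful reader to the outlier. A proportion could be derived from that listing. This lowers the stakes, but a proportion built by hand after the results are seen has no pre-set threshold.

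On the second rule, dropping `<x` with x above 400 is reasonable, since such a result says little. The objection fails only for `>x`.

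**Conclusion.** The point holds as a low-severity improvement. The plan has no summary of the share suppressed. If its chart is a raw-copies mean, it can rank strata opposite to that share, in about 2% to 24% of untied pairs under the assumed inputs. The range rests on invented stratum sizes, viraemic shares and loads, and on the inferred statistic. A log10 mean does better (0% to 8%) but can also misrank, which is why it should be secondary.

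The second rule is inconsistent with the third for `>x` results, with unknown and possibly nil effect. A reader might infer that it biases the efficacy results; the documents give no basis for saying such results occurred.

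Nor do the documents support a claim that any inference is invalid. The HIV-RNA analysis is descriptive, no test is assigned to it, adverse drug reactions are the primary items, and CD4 is unaffected.

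Three side notes carry little weight. A `<400` result meets the second rule although 399 is the stated substitute, but the 399 period ends in March 2008, before approval. The 39-to-19 switch moves a raw mean by at most 20 copies (log10(39/19) = 0.31 without a common floor). Month 0 can be on treatment where the first dose date was reset to the approval date.

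**What to change.** 1. At each time point and stratum, report n and the proportion suppressed at one fixed threshold no lower than the 39/40-copy limit, with a 95% CI. With ≤40 copies, a result recorded as 40 under the SAP's own example counts as suppressed.
2. State the centre statistic and scale of the chart and table. Show log10 copies as the secondary, continuous summary, with every result at or below the threshold set to one common floor (for example 40) in all years and sites. Note that its ranking can differ from the proportion. A median is possible but is uninformative when most patients are suppressed.
3. Restrict the second rule to `<x` results. Keep `>x` results at their bound and count them as not suppressed when x is at or above the threshold. This matters for item 1: if 10% of patients are viraemic and 20% of those results are dropped, the share suppressed reads 0.90/(1 − 0.10×0.20) = 91.8% instead of 90.0% (both inputs assumed).
4. Treat `<x` results whose substituted value exceeds the threshold as indeterminate for the proportion. Report the number missing or indeterminate per time point and stratum.

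The cost is SAP wording and reprogramming one table and chart; no new data are needed. Resolution below the threshold is given up, and some `<x` results stay indeterminate.
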